10.3.1.4 Safety variables

Safety and tolerability variables are:

- Adverse events (Section 9.6.1), including
 - SAEs, AEs, treatment-emergent AEs and AEs of special interest, including AV blocks > I°
 - SAEs and AEs leading to discontinuation of interruption of study drug, including AV blocks in particular
- Laboratory abnormalities (Section 9.6.3.1), measured values and change from baseline, in particular
 - Change in renal function measured by eGFR change from baseline
 - Change in liver function measured by bilirubin (total and fractions), AST and ALT from baseline
- 12-ECG abnormalities (Section 9.6.3.3) and PR interval duration
- Blood pressure and heart rate (Section 9.6.3.4); measured values and change from baseline
- Number of clinically significant findings in ECG and / or AVIVO device report

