9.6.3 Further safety

9.6.3.1 Laboratory evaluations

All laboratory evaluations will be done by central laboratory. Additional re-tests for liver monitoring (Section 9.6.3.6) will be done locally.

Hematology: erythrocytes, hemoglobin, hematocrit, MCV, MCH, MCHC, reticulocytes, leukocytes, differential blood count, platelets

Clinical chemistry: aspartate aminotransferase (AST), alanine aminotransferase (ALT), alkaline phosphatase (AP), gamma glutamyl transpeptidase (GGT), lactate dehydrogenase (LDH), creatine kinase (CK), amylase, lipase, glucose, cholesterol (HDL, LDL, total), triglycerides, creatinine, urea, uric acid, bilirubin, total protein, albumin, sodium, potassium, calcium, chloride, magnesium, anorganic phosphate

Coagulation: partial thromboplastin time (PTT), international normalized ratio (INR)

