9.6.3.6 Liver function monitoring

Any patient with an ALT or AST > 3 x ULN or alkaline phosphatase (AP) >2 x ULN must be re-tested as soon as possible but at the latest within 48-72 hours of the investigator becoming aware of the result. This re-testing and any subsequent testing based on elevated levels should include measurement of ALT, AST, total and direct bilirubin, and AP, and will be assessed by local laboratory. Every effort should be made to clarify the etiology of elevated levels. Patient management is at the discretion of the investigator but the treating physician may continue the study drug during retesting. Liver function test monitoring should be performed as above for all patients even if the study drug is interrupted until tested values have normalized or returned to patient's baseline. If close liver monitoring is not possible then the patient should discontinue study medication.

For ALT or AST > 3 x ULN concurrent with a total bilirubin > 2 x ULN, every effort should be made to clarify any possible underlying disease(s).

The frequency of liver function tests based on re-test values is shown in [Table 9-3](#).

Table 9-3: Liver function monitoring

ALT, AST or AP level at re-test	Frequency	Further notice
ALT or AST > 3 x ULN	2-3 times a week	Obtain details on liver related symptoms and exclude other causes of liver enzyme elevations
ALT or AST ≤ 3 x ULN	Once a week	Until return to normal or patient baseline levels
AP >2 x ULN	2-3 times a week	Obtain details on liver related symptoms and exclude other causes of liver enzyme elevations

Abbreviations: ALT = alanine aminotransferase; AP = alkaline phosphatase; AST = aspartate aminotransferase; ULN = upper limit of normal

Discontinuation of treatment should be considered if:

- ALT or AST > 8 x ULN
- ALT or AST > 5 x ULN for more than 2 weeks
- ALT or AST > 3 x ULN and (total bilirubin >2 x ULN or INR > 1.5)
- ALT or AST > 3 x ULN with the appearance of fatigue, nausea, vomiting, right upper quadrant pain or tenderness, fever, rash, and / or eosinophilia (> 5%)
- AP > 2 x ULN or ALT/AP < 2 for more than 2 weeks if other causes of cholestasis are excluded

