10.3.2.4 Analysis of the safety variables

If not indicated otherwise, evaluation of safety variables will be done using the SAF.

Adverse events

The adverse events (AE) analysis will be performed as treated in the SAF. All tabulations will be descriptive only.

Individual listings of AEs will be provided. The incidence of treatment-emergent AEs and drug-related (treatment-emergent) AEs will be tabulated by treatment group using MedDRA terms. Separate tables and listing for serious AEs and death will be provided.

Further safety parameters

The safety evaluation of laboratory data will include:

- Descriptive analysis of continuous laboratory parameters, and their changes from baseline by visit and treatment group.
- Incidence rates of treatment-emergent laboratory values outside of normal range by treatment group.
- Listings of laboratory data out of normal range.

Vital signs and their changes from baseline will be analyzed descriptively by visit and by treatment group.

ECG-findings (like AV-conduction abnormalities) will be summarized in frequency tables. A table displaying the number of patients with AV-block > I° will be provided.

Data from the AVIVO monitoring will be summarized; details will be described in the SAP.

Summary statistics and figures of heart rate and blood pressure (systolic, diastolic, and mean arterial pressure) will be created.

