6.3.5 Clinical laboratory evaluations

All laboratory evaluations will be done by central laboratory.

Hematology: erythrocytes, hemoglobin, hematocrit, MCV, MCH, MCHC, reticulocytes, leukocytes, differential blood count, platelets

Clinical chemistry: aspartate aminotransferase (AST), alanine aminotransferase (ALT), alkaline phosphatase (AP), gamma glutamyl transpeptidase (GGT), lactate dehydrogenase (LDH), creatine kinase (CK), amylase, lipase, glucose, cholesterol (HDL, LDL, total), triglycerides, creatinine, urea, uric acid, bilirubin, total protein, albumin, sodium, potassium, calcium, chloride, magnesium, anorganic phosphate

Coagulation: partial thromboplastin time (PTT), international normalized ratio (INR)

The safety evaluation of laboratory data will include:

- Descriptive analysis of continuous laboratory parameters, and their changes from baseline by visit and treatment group.
- Incidence rates of treatment-emergent laboratory values outside of normal range by treatment group.
- Listings of laboratory data out of normal range.

Laboratory abnormalities will be summarized in table of change from baseline by visit and treatment:

- Change in renal function measured by eGFR change from baseline
- Change in liver function measured by bilirubin (total and fractions), AST and ALT from baseline

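### Laboratory liver values are counted by arm only as outside the normal range; a table at the protocol's own multiples of ULN, with the combined ALT/AST and bilirubin or INR criterion, would complement that count

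*Protocol*

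**What the plan says.** Protocol 9.6.3.6 works in multiples of ULN. The re-test rule reads "Any patient with an ALT or AST > 3 x ULN or alkaline phosphatase (AP) >2 x ULN must be re-tested". The conditions for considering discontinuation include "ALT or AST > 8 x ULN", a level above 5 x ULN lasting more than two weeks, ALT or AST above 3 x ULN with listed symptoms, an AP criterion, and the combined condition "ALT or AST > 3 x ULN and (total bilirubin >2 x ULN or INR > 1.5").

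The analysis does not use these levels. Protocol 10.3.1.4 and SAP 6.3.5 both name the liver variable as "Change in liver function measured by bilirubin (total and fractions), AST and ALT from baseline". Protocol 10.3.2.4 and SAP 6.3.5 plan three laboratory outputs. One summarises each analyte as a continuous measure, with its change over time in every arm. Another is the only patient count, given as "Incidence rates of treatment-emergent laboratory values outside of normal range by treatment group". The last is a set of individual records, which the protocol calls "Listings of laboratory data out of normal range". No liver event is among the adverse events of special interest (protocol 9.6.1.6, SAP 6.3.3).

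On re-tests, protocol 9.6.3.1 says "Additional re-tests for liver monitoring (Section 9.6.3.6) will be done locally", and SAP 4.5.3 repeats this. SAP 6.3.5 describes all laboratory evaluations as central. SAP 4.5.2 admits unscheduled results to abnormality tables, and SAP 4.5.3 admits unscheduled laboratory data to summary tables.

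**The concern.** The final target dose depends partly on safety (protocol 10.3.2.2, SAP 6.2.1.2). Safety is descriptive and untested (SAP 6.3), so the choice of table decides what a reader can compare across doses. A count at the edge of the normal range gives the same weight to a trivial ALT rise and to one that would trigger re-testing or a discontinuation decision. It also does not separate high values from low ones.

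If one dose produced a few large elevations, the excess could be hard to see against mild abnormalities in a heart failure population. Whether ALT or AST and bilirubin rose in the same patient could not be read from any planned table, because each analyte is summarised separately.

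**Working it through.** **Denominators.** Protocol 10.4 gives 288 / 0.75 = 384 randomised. With the ratio 3:1:2:2:2:2, 384 / 12 = 32 per unit, so placebo has 96, the 5 mg arm 32, and the 10, 20, 30 and 40 mg arms 64 each. This reproduces the stated arm sizes. The safety set needs at least one dose, so 64 v 96 is a slight upper bound for one dose arm against placebo.

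**Assumptions not in the documents.** The documents give no liver rates. I take ALT or AST above 3 x ULN as 0.5% on placebo and 5.5% on one dose, an excess of 5 points. The background share b of patients with any value above ULN is 10-30%. Because the planned count is of treatment-emergent values, I also take b = 2-5%.

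**Yardstick.** One-sided Fisher p <= 0.10, which is not in the plan and serves only to measure how well a table separates the arms. The chance is the sum over x and y of Bin(x; 64, p1) x Bin(y; 96, p0), taken where P(H >= x) <= 0.10. H is hypergeometric: 64 draws from 160 patients of whom x + y are cases.

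**Counted above 3 x ULN.** 5.5% v 0.5% gives 59%. With a higher background and the same excess, 6% v 1% gives 56% and 7% v 2% gives 50%.

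**Counted above ULN, two ways the dose might act.**

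- Model A, large elevations only: p1 = b + 0.05 x (1 - b).
- Model B, the whole log-normal ALT distribution shifts. The shift that takes 0.5% to 5.5% above 3 x ULN is 2.576 - 1.598 = 0.978 SD, and p1 = 1 - Phi(z - 0.978), where z is the normal quantile with upper tail b. For b = 10%, z = 1.282 and p1 = 1 - Phi(0.304) = 38%.

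| b (placebo) | Model A: p1 | Model A: chance | Model B: p1 | Model B: chance |
|---|---|---|---|---|
| 2% | 6.9% | 49% | 14% | 94% |
| 5% | 9.75% | 37% | 25% | 99% |
| 10% | 14.5% | 26% | 38% | over 99% |
| 20% | 24% | 19% | 55% | over 99% |
| 30% | 33.5% | 16% | 67% | over 99% |

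The figure to compare with every row is 59%. Model A falls below it in each row; Model B lies above it in each row.

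**A larger excess under Model A.** With 9% v 1% above 3 x ULN and a one-sided 5% level, the chance is 69%. The same 8-point excess counted above ULN gives 30%, 19% and 14% for b = 10%, 20% and 30%. The ratio of rates falls from 9.0 to between 1.7 and 1.2.

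**The case against.** The plan is less blind than a first reading suggests.

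- **Large elevations do not show only in listings.** Abnormal laboratory findings can be adverse events (protocol 9.6.1.1). SAP 6.3.3 tabulates treatment-emergent events, serious events and events leading to withdrawal or interruption by arm. Continuous summaries include the maximum (protocol 10.3.2, SAP 4.1), so a very high ALT at a scheduled visit can appear as that arm's maximum. This stands. These outputs still give no rate by dose at a stated level: event reporting depends on the investigator, and a maximum describes one patient.
- **AP is not left out of the analysis.** A reader might infer that from the liver line. That line gives particular examples within all laboratory abnormalities, and AP is in the chemistry panel, so it gets the same generic outputs as ALT and AST. Only a count at its 2 x ULN trigger is missing.
- **Exclusion of local re-tests is not shown.** A reader might infer it from SAP 6.3.5, but SAP 4.5.2 and 4.5.3 bring unscheduled results into tables. Whether local values count as unscheduled, and against which ULN, is unclear. That is an ambiguity, not an exclusion.
- **Threshold tables may exist elsewhere.** SAP 4.1 refers displays to sponsor standards and SAP 6.2.1.5 mentions a separate TLF specification, neither of which is available here. The point is therefore limited to the protocol and SAP text.
- **Stakes.** The documents identify no hepatic signal, and an unblinded external DMC reviews safety. This limits the weight of the point but does not supply the missing count.

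**Conclusion.** The point holds as a cheap improvement to reporting. Neither document plans a count of laboratory values by arm at ALT or AST above 3, 5 or 8 x ULN, at AP above 2 x ULN, or at the combined ALT/AST and bilirubin or INR criterion. This rests on the text alone.

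The size rests on assumed rates. If a dose adds large elevations without mild ones, the normal-range count separates the arms in 16-49% of trials over the backgrounds examined, against 59% for a count above 3 x ULN. A reader might infer that the normal-range count always dilutes a dose-related signal. The documents do not support that: if the dose shifts the whole distribution, the normal-range count does better (94% or more, against 59%). The documents do not say which pattern to expect, so both tables are worth having. The primary efficacy analysis is unaffected.

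**What to change.** In SAP 6.3.5, add one descriptive table by treatment group in the safety set, alongside the normal-range count. It counts patients whose maximum value after the first dose, including unscheduled values, is:

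- ALT or AST above 3, above 5 and above 8 x ULN;
- AP above 2 x ULN;
- ALT or AST above 3 x ULN with total bilirubin above 2 x ULN or INR above 1.5.

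Show baseline status. Label the entries as peak-value counts, because the duration and symptom conditions in protocol 9.6.3.6 are not reproduced. State whether local re-test values enter and, if so, that they are scaled by the local laboratory's ULN.

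The cost is one extra table, mostly from data already collected. If local re-tests are included, their results and ULN must be in the database. No clinical rule changes.

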10.3.2 Statistical and analytical plans

All data will be listed and all variables will be summarized by means of descriptive statistics according to their type.

Summaries by treatment group using appropriate descriptive statistics will be provided for all study variables including demographic and baseline characteristics. Summary statistics will be presented for the original data as well as for the difference to baseline. Descriptive statistics such as arithmetic mean (or geometric mean, if applicable), median, standard deviation, quantiles, minimum, and maximum will be used to summarize continuous variables. Counts and percentages will be used to summarize categorical variables. Life tables and Kaplan-Meier estimates will be used to summarize time-to-event variables. Graphical data displays may also be used to summarize the data. Confidence intervals will be provided at a 2-sided level of 90% unless otherwise stated.

For this combined proof-of-concept and dose-finding study, an overall one-sided type I error level of 5% is planned to be used. The type I error will be controlled for the primary analysis of the primary variables.

There will be no formal control of the type I error for secondary or explorative analyses of the primary variables and any analysis of other efficacy variables.

10.3.2.1 Subgroups

In order to assess the homogeneity of the dose response across the most important prognostic and predictive factors, subgroup analyses will be performed.

'Key' subgroups comprise:

- LVEF(%) at baseline: ≤ 25 vs. > 25
- NT-proBNP (pg/ml) at baseline: \leq median vs. $>$ median
- NYHA class at baseline: II vs. III / IV
- Prior β -blocker: yes vs. no

Truly exploratory analyses, i.e., mainly summary statistics, will be provided for a spectrum of demographic, disease and clinical characteristics, including

- Age (years): < 65 , $65-75$, > 75
- Gender: male vs. female
- Race: White vs. non-white
- Region: North America / South America / West Europe / East Europe / Asia
- Region: Japan vs. rest-of-the-world (analysis to be included in reports specific for Japan only)
- BMI at baseline (kg/m^2): ≤ 30 vs. > 30
- Time of CHF diagnosis to randomization (months): ≤ 3 vs. > 3
- Prior hospitalization for heart failure: yes vs. no
- Etiology of CHF: ischemic vs. non-ischemic
- Diabetes: yes vs. no
- Atrial fibrillation: yes vs. no
- Hypertension: yes vs. no
- Prior CHF medication:
 - Prior β -blocker in max tolerated dose: yes vs. no
 - Prior use of ivabradine: yes vs. no
 - Prior use of aldosterone antagonist: yes vs. no
 - Prior use of ACE inhibitor: yes vs. no
 - Prior use of ARB: yes vs. no
 - Prior use of angiotensin receptor-neprilysin inhibitor (ARNI): yes vs. no
- Estimated GFR ($\text{ml}/\text{min}/1.73 \text{ m}^2$): ≤ 60 vs. > 60

Further details will be described in detail in the SAP.

10.3.2.2 Analysis of the primary efficacy variables

This section was changed in Amendment 2, see Section 15.1 for details.

For both primary efficacy variables, it is planned to perform a test for a dose-response signal, respectively, under the assumption of a nearly monotone dose-response relationship in the dose range considered. The MCP-Mod method (46) combining multiple comparison procedures (MCP) principles with modeling techniques will be used for the primary statistical analysis of the primary efficacy variables. This method allows the flexibility of modeling for dose estimation, while preserving the robustness to model misspecification associated with MCP procedures.

Two primary variables have been defined to better evaluate multiple dimensions of the treatment effect, thereby adding a source of multiplicity. The overall outcome of the primary efficacy analysis will be considered positive if at least one of the two null hypotheses related to the primary efficacy variables can be rejected. The Hochberg (step-up) procedure will be applied to control the family-wise error rate (FWER):

Consider the null hypotheses for LVEF, $H_{0,LVEF}$, and for NT-proBNP, $H_{0,NT-proBNP}$, and their associated raw p-values p_{LVEF} and $p_{NT-proBNP}$. The Hochberg test is performed using the following steps:

1. If $\max(p_{LVEF}, p_{NT-proBNP}) \leq \alpha = 0.05$, both null hypotheses $H_{0,LVEF}$ and $H_{0,NT-proBNP}$ will be rejected and the procedure stops.
2. If $\max(p_{LVEF}, p_{NT-proBNP}) > \alpha = 0.05$ and $\min(p_{LVEF}, p_{NT-proBNP}) \leq \alpha/2 = 0.025$, the null hypothesis related to the larger p-value $\max(p_{LVEF}, p_{NT-proBNP})$ will be accepted and the null hypothesis related to the smaller p-value $\min(p_{LVEF}, p_{NT-proBNP})$ will be rejected.
3. Otherwise, both null hypotheses $H_{0,LVEF}$ and $H_{0,NT-proBNP}$ will be accepted.

Assumptions

Five active doses of neladenoson bialanate will be used in this study: 5 mg, 10 mg, 20 mg, 30 mg, and 40 mg, as well as a placebo arm corresponding to a 0 mg dose.

The measurements of the primary efficacy variables are assumed to be normally distributed with the same standard deviation σ and independent between patients, respectively.

LVEF: The following assumptions were made for the absolute change from baseline in LVEF over 20 weeks:

- the expected mean effect under the placebo dose is conservatively assumed as an absolute increase from baseline of up to $\Delta = 2\%$ with a standard deviation of $\sigma = 7\%$
- while the maximum observable mean effect under neladenoson bialanate within the dose range considered is assumed as an absolute increase of $\Delta = 5\%$ with a standard deviation of $\sigma = 7\%$.

This results in an expected maximum effect size of $(5-2)/7 = 3/7 = 0.43$ under conservative assumptions. Note that the threshold of clinical relevance is an absolute difference of 3% in the change from baseline over the placebo control group.

NT-proBNP: The following assumptions were made for the absolute change from baseline in the log-transformed NT-proBNP over 20 weeks:

- the expected mean effect under the placebo dose is assumed as an absolute decrease from baseline of $-0.105 \log(\text{pg/mL})$ with a standard deviation of $\sigma = 0.85 \log(\text{pg/mL})$, which is equivalent to a 10% relative reduction from a mean of 2,500 pg/mL at baseline.
- while the maximum observable mean effect under neladenoson bialanate within the dose range considered is assumed as an absolute decrease from baseline of $-0.357 \log(\text{pg/mL})$ with a standard deviation of $\sigma = 0.85 \log(\text{pg/mL})$, which is equivalent to a 30% relative reduction from a mean of 2,500 pg/mL at baseline.

It is assumed that the respective primary response efficacy variable, denoted as Y , is observed for the 6 parallel groups corresponding to doses levels: (placebo =) $d_1 < d_2 < \dots < d_k$, where $k = 6$.

For patient j within treatment group i the response can then be described by the following model:

$$Y_{ij} = f(d, \boldsymbol{\theta}) + \varepsilon_{ij}, \quad \varepsilon_{ij} \sim N(0, \sigma^2), \quad i = 1, \dots, k, \quad j = 1, \dots, n_i,$$

[figure not shown]
where $f(\cdot)$ is parameterized by a vector of parameters $\boldsymbol{\theta}$ and ε_{ij} is the error term.

A candidate set with $M=5$ different dose response shapes $f(\cdot)$ based on four models was chosen for the MCP-Mod method. Table 10–1 displays the response expressions for the shapes in the candidate sets for both, change in LVEF and change in log-transformed NT-proBNP. Figure 10–1 shows the corresponding dose-response shapes for change in LVEF. The model parameters were obtained through discussions with experts in the clinical team, taking prior beliefs and uncertainty into account. The dose-response shapes for NT-proBNP are equivalent to those for LVEF but with decreasing trends.

Table 10–1: Dose-response shapes used in the candidate set

Model	Response as function of dose d	
	LVEF	NT-proBNP
Linear	$2 + 0.075d$	$-0.105 - 0.0063d$
Sigmoidal E_{\max} 1	$2 + 3.007689d^4 / (9^4 + d^4)$	$-0.105 - 0.2526d^4 / (9^4 + d^4)$
Sigmoidal E_{\max} 2	$2 + 3.375d^3 / (20^3 + d^3)$	$-0.105 - 0.2835d^3 / (20^3 + d^3)$
E_{\max}	$2 + 3.09375d / (1.25 + d)$	$-0.105 - 0.2599d / (1.25 + d)$
Quadratic	$2 + 0.2d - 0.00333d^2$	$-0.105 - 0.0168d + 0.00028d^2$

Figure 10–1: Dose-response shapes used in the candidate set for change in LVEF

Abbreviations: LVEF = left ventricular ejection fraction

Based on the standardized versions of the models in the candidate set and the sample size allocation planned for this study, the optimum contrast coefficients for the 5 contrast tests on the dose-response shapes can be derived for both primary variables.

Analysis

Step 1: Detection of dose-response signal

For detecting an overall trend, or a dose-response signal, each of the $M=5$ dose-response shapes in the candidate set will be tested, using a single contrast test based on the updated version of contrast coefficients taking the actual sample sizes per treatment group into account.

For each model m , $m = 1, \dots, 5$, in the candidate set

the null hypothesis $H_{0m}: c_m \mu_m^0 = 0$

will be tested against

the respective 1-sided alternative hypothesis $H_{1m}: c_m \mu_m^0 > 0$,

where $\mu_m^0 = (\mu_{m1}^0, \dots, \mu_{m6}^0)' = (f_m^0(d_1, \theta_m^0), \dots, f_m^0(d_6, \theta_m^0))'$ and

f^0 is the standardized version of the dose-response model $f(d, \theta) = \theta_0 + \theta_1 f^0(d, \theta^0)$. In this parameterization, θ_0 is a location parameter and θ_1 is a scale parameter such that only θ^0 determines the shape of the model function.

A “proof-of-concept” dose-response relationship is detected if at least one single contrast test, is statistically significant, while controlling the family-wise error rate at level α . The smallest of the corresponding adjusted p-values will be used for the Hochberg test.

This analysis will be performed for the FAS and PPS populations, where the PPS analysis is the primary analysis.

If no candidate model is statistically significant, the procedure stops, indicating that a dose-response relationship cannot be established from the observed data.

Out of the statistically significant models in the candidate set a best model can be selected for the next step: modeling and estimation.

Step 2: Modeling and estimation of target doses

If a dose-response signal is established, the selected dose-response model(s) will be fitted to the observed data to estimate the model parameters.

The estimated dose-response model will be plotted against the doses including 90% confidence bands. Once the dose-response model has been successfully fitted to the data, target dose(s) of interest are estimated. Given a clinically relevant effect Δ , a minimum effective dose (MED_{Δ}) associated with model $f(d, \theta)$ is defined as

$$MED_{\Delta} = \operatorname{argmin}_{d \in (d_1, d_6]} \{f(d, \theta) \geq f(d_1, \theta) + \Delta\}.$$

Estimates of MED_{Δ} will be calculated for a clinically relevant change in LVEF assumed as $\Delta = 3\%$ and potentially a plausible range of Δ values which will be defined in the SAP. Estimation for change in log-transformed NT-proBNP will be performed analogously, ensuring an adequate back-transformation to allow for better interpretability of the results. In addition, estimates considering confidence bounds for the predicted value at a certain dose may be used. The final choice of the target dose depends on the evaluation of the primary efficacy variables and other efficacy variables, as well as safety considerations.

Modeling and estimation will be performed for the FAS and PPS populations as well as for relevant subgroups.

Further details will be described in the SAP.

As a secondary analysis pairwise comparisons of the active neladenoson bialanate dose groups with the placebo group will be performed without controlling the family-wise error rate.

